8.3 Subgroup Analyses

For the mean change from baseline in MADRS total score, the same MMRM analysis as that of the primary endpoint will be performed for each of the following subgroups.

For CYP2D6 genotype, all subjects in the placebo group will be included in each subgroup.

- Sex (male, female)
- Age (< 55 , ≥ 55)
- Body weight (\leq median, $>$ median)
- BMI (\leq median, $>$ median)

- CYP2D6 genotype (phenotype) (PM, IM, EM)
- Duration (in months) of the current major depressive episode (\leq median, $>$ median)
- Age at initial onset (\leq median, $>$ median)
- Duration (in months) of major depression from initial onset (\leq median, $>$ median)
- Baseline MADRS total score (< 30 , ≥ 30)
- Baseline CGI-S (\leq median, $>$ median)
- Baseline HAM-D 17-item total score (\leq median, $>$ median)
- Baseline Apathy Scale total score (\leq median, $>$ median)
- Baseline MADRS-S total score (\leq median, $>$ median)
- Baseline MADRS anhedonia factor score (\leq median, $>$ median)
- DSM-5 diagnosis (single episode, recurrent episode)
- DSM-5 severity (mild, moderate, severe)
- Specifiers (not applicable, applicable, applicable if [with anxious distress, with mixed features, with melancholic features, with atypical features, with mood-congruent psychotic features, with mood-incongruent psychotic features, with catatonia, peripartum onset, seasonal pattern])
- Number of major depressive episodes (1, 2, 3, 4, ≥ 5)
- Prior medications (antidepressants) for the current major depressive episode (yes or no)
- Prior medications (antianxiety agents) (yes or no)
- Prior medications (hypnotic agents) (yes or no)

8.4 Exploratory or Other Analyses

The Cochran Mantel Haenszel (CMH) Row Mean Scores test of CGI-I scores will be performed on LOCF dataset to compare the OPC-64005 20-mg group and the placebo group. The mean in each treatment group and the mean difference between each OPC-64005 group and the placebo group with their two-sided 95% CIs will be determined. The same analysis will be performed on the OC dataset.

For MADRS total score, HAM-D 17-item total score, Apathy Scale total score, CGI-S, MADRS-S total score, and MADRS anhedonia factor score, descriptive statistics of measurement values and changes from baseline at each time point will be calculated for each treatment group in FAS. For CGI-I, descriptive statistics of measurement values at each time point will be calculated for each treatment group in FAS.

For the mean change from baseline in each subscale of MADRS and MADRS-S, the same MMRM analysis as that of the primary endpoint will be performed in FAS. For the mean change from baseline in each subscale of HAM-D 17-item and Apathy Scale, the

same analysis as that of HAM-D 17-item total score will be performed. For each subscale of MADRS, MADRS-S, HAM-D 17-item, and Apathy Scale, descriptive statistics of measurement values and changes from baseline at each time point will be calculated for each treatment group.

9 Safety Analyses

The safety analysis will be performed on the safety analysis set. Baseline is the last data obtained after the start of IMP administration in the placebo-lead in period and before the start of double-blind IMP administration.

9.1 Extent of Exposure

The frequency distribution of treatment period (in days) in the double-blind treatment period (1-7, 8-14, 15-21, 22-28, 29-35, 36-42, > 42) will be determined by treatment group and for the overall OPC-64005 group.

9.2 Adverse Events

All AEs will be coded by system organ class (SOC) and ICH's Medical Dictionary for Regulatory Activities (MedDRA) Version 24.1 preferred term (PT). The incidence of the following events will be summarized by treatment group and for the overall OPC-64005 group. In tabulation by severity, if the same AE occurs more than once in the same subject, the severest event will be used.

- Adverse events occurring after the start of double-blind IMP administration (treatment-emergent adverse events [TEAEs])
- TEAEs by severity
- TEAEs with an outcome of death
- Serious TEAEs
- TEAEs leading to discontinuation of the IMP
- TEAEs of special interest (drug eruption)
- TEAEs occurring in at least 2% of subjects in the OPC-64005 20-mg group and more frequently than in the placebo group
- TEAEs by time of initial onset (Day) (1-7, 8-14, 15-21, 22-28, 29-35, 36-42, > 42)
TEAEs of special interest (drug eruption) are defined as IMP-related TEAEs whose coded PTs are included in both Standardised MedDRA Queries (SMQ) “Hypersensitivity” and SOC “skin and subcutaneous tissue disorders.”

Treatment-emergent AEs potentially causally related to the IMP will also be summarized in the same manner.

9.3 Clinical Laboratory Data

Descriptive statistics of measurement values and changes from baseline at each time point will be calculated by treatment group and for the overall OPC-64005 group for each laboratory test item of continuous data.

Each laboratory test item of continuous data will be classified into below the lower limit of the reference range, within the reference range, or above the upper limit of the reference range based on the reference ranges of the central laboratory, and a shift table from baseline will be generated by treatment group and for the overall OPC-64005 group.

For each laboratory test item of qualitative data, a shift table from baseline will be generated by treatment group and for the overall OPC-64005 group.

The number and proportion of subjects who do not meet the criteria for clinically significant laboratory values (Appendix 2) at baseline and meet the criteria after the start of IMP administration will be determined by treatment group and for the overall OPC-64005 group. A listing of these subjects will be provided.

The numbers and proportions of subjects with values for alanine aminotransferase (ALT), aspartate aminotransferase (AST), and total bilirubin (TBL) after the start of IMP administration meeting Hy's Law criteria (ALT or $AST \geq 3 \times$ the upper limit of normal [ULN] and $TBL \geq 2 \times$ ULN) will be determined by treatment group and for the overall OPC-64005 group. A listing of these subjects will be provided.

The numbers and proportions of subjects with a prolactin value not meeting the criteria of $> 1 \times$ ULN, $> 2 \times$ ULN, or $> 3 \times$ ULN at baseline and meeting the criteria after the start of IMP administration will be determined by sex for each treatment group and the overall OPC-64005 group. A listing of these subjects will be provided.

The numbers and proportions of subjects with values of fasting low-density lipoprotein (LDL) cholesterol, high-density lipoprotein (HDL) cholesterol, triglyceride, and blood glucose after the start of IMP administration meeting the criteria for changes in glucose and lipid metabolism-related parameters (Table 9.3-1) will be determined by baseline value for each treatment group and the overall OPC-64005 group. A listing of these subjects will be provided.

Table 9.3-1 Changes in Glucose and Lipid Metabolism-related Parameters		
LAB PARAMETER	BASELINE	ANYTIME POST BASELINE
LDL Cholesterol, Fasting (mg/dL)	Borderline 100-<160 Normal/Borderline <160 Normal <100 Any Value	High >=160 High >=160 Borderline/High >=100 Increased >=30
HDL Cholesterol, Fasting (mg/dL)	Normal >=40 Any Value	Low <40 Decreased >=20
Triglycerides, Fasting (mg/dL)	Normal <150 Borderline 150-<200 Normal/Borderline <200 Normal <150 Normal/Borderline/High <500 Any Value	High 200-<500 High 200-<500 High 200-<500 Borderline/High/Very High >=150 Very High >=500 Increased >=50
Glucose Fasting, Serum (mg/dL)	Normal <100 Impaired 100-<126 Normal/Impaired <126 Any Value	High >=126 High >=126 High >=126 Increased >=10

The number and proportion of subjects who do not meet the diagnostic criteria for metabolic syndrome (Table 9.3-2) at baseline and meet the criteria after the start of IMP administration will be determined by treatment group and for the overall OPC-64005 group. A listing of these subjects will be provided.

Table 9.3-2 Diagnostic Criteria for Metabolic Syndrome	
Description	Metabolic Syndrome Criteria (Health, Labour and Welfare Ministry of Japan)
Central obesity	Waist Circumference ≥ 85 cm (Male), ≥ 90 cm (Female)
Dyslipidemia	Triglycerides, Fasting ≥ 150 mg/dL and/or HDL, Fasting <40 mg/dL
Supine blood pressure	Systolic ≥ 130 mmHg and/or Diastolic ≥ 85 mmHg
Glucose fasting, serum	≥ 110 mg/dL
Metabolic syndrome	Met central obesity criteria and 2 of 3 other criteria at a visit

9.4 Vital Sign Data

For each item of vital signs (by position for blood pressure and pulse rate), descriptive statistics of measurement values and changes from baseline at each time point will be calculated by treatment group and for the overall OPC-64005 group.

The number and proportion of subjects who meet the criteria for clinically significant vital signs (Appendix 1) will be determined by treatment group and for the overall OPC-64005 group. A listing of these subjects will be provided.

9.5 Physical Examination Data

Listings of physical examination findings will be provided.

9.6 Electrocardiogram Data

For heart rate, PR interval, RR interval, QRS interval, QT interval, and QTc (QTcF), descriptive statistics of measurement values and changes from baseline at each time point will be calculated by treatment group and for the overall OPC-64005 group.

For normal/abnormal assessment of 12-lead ECG, a shift table from baseline will be generated by treatment group and for the overall OPC-64005 group.

For QTc (QTcF), the number and proportion of subjects with measurement values of > 450 msec, > 480 msec, and > 500 msec (ie, subjects who do not meet these criteria before the start of double-blind IMP administration and meet the criteria after the start of double-blind IMP administration) and the number and proportion of subjects with changes from baseline of > 30 msec and > 60 msec will be determined by treatment group and for the overall OPC-64005 group. The number and proportion of subjects with measurement values of > 450 msec and with percent change from baseline of > 10% will also be determined by treatment group and for the overall OPC-64005 group.

The number and proportion of subjects who meet the criteria for clinically significant ECG (Appendix 3) will be determined by treatment group and for the overall OPC-64005 group. A listing of these subjects will be provided.

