9.4.2.2 Clinical Laboratory Data

Descriptive statistics of measurement values and changes from baseline at each time point will be calculated by treatment group and for the overall OPC-64005 group for each laboratory test item of continuous data.

Each laboratory test item of continuous data will be classified into below the lower limit of the reference range, within the reference range, or above the upper limit of the reference range based on the reference ranges of the central laboratory, and a shift table from baseline will be generated by treatment group and for the overall OPC-64005 group.

For each laboratory test item of qualitative data, a shift table from baseline will be generated by treatment group and for the overall OPC-64005 group.

The number and proportion of subjects who meet the criteria for clinically significant laboratory value will be determined by treatment group and for the overall OPC-64005 group.

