9.4.2.4 Electrocardiogram Data

For heart rate, PR interval, RR interval, QRS interval, QT interval, and QTc (QTcF), descriptive statistics of measurement values and changes from baseline at each time point will be calculated by treatment group and for the overall OPC-64005 group.

For normal/abnormal assessment of 12-lead ECG, a shift table from baseline will be generated by treatment group and for the overall OPC-64005 group.

For QTc (QTcF) at each time point, the number and proportion of subjects with measurement values after double-blind IMP treatment of > 450 msec, > 480 msec, and > 500 msec, and the number and proportion of subjects with changes from baseline of > 30 msec and > 60 msec will be calculated by treatment group and for the overall OPC-64005 group.

The number and proportion of subjects who meet the criteria for clinically significant ECG will be determined by treatment group and for the overall OPC-64005 group.

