9.7.2 Columbia-Suicide Severity Rating Scale

The number and proportion of subjects at each time point and for the entire period after the start of double-blinded IMP administration (including post-treatment observation, discontinuation, and unscheduled visits) will be determined by treatment group and for the overall OPC-64005 group for each item (suicidality, suicidal ideation, suicidal behavior, completed suicide, emergence of suicidal ideation, emergence of serious suicidal ideation, worsening of suicidal ideation, and emergence of suicidal behavior). A listing of subjects with emergence of suicidal ideation, emergence of serious suicidal ideation, worsening of suicidal ideation, and emergence of suicidal behavior will be provided. The same tabulation will be performed for each category of suicidal ideation and suicidal behavior.

- Suicidality: “Yes” to any question of suicidal ideation or suicidal behavior
- Suicidal ideation: “Yes” to any question of suicidal ideation
- Suicidal behavior: “Yes” to any question of suicidal behavior
- Emergence of suicidal ideation: Suicidal ideation is absent at baseline and present after baseline.
- Emergence of serious suicidal ideation: Suicidal ideation is absent at baseline and present with an intensity of 4 or 5 after baseline.
- Worsening of suicidal ideation: Increase in the intensity of suicidal ideation after baseline compared with baseline.
- Emergence of suicidal behavior: Suicidal behavior is absent at baseline and present after baseline.

10 Pharmacokinetic Analyses

For the plasma concentrations of OPC-64005 and OPC-144013, only listings of data will be generated without tabulation.

11 Pharmacodynamic Analyses

Not applicable.

12 Pharmacogenomic Analyses

CYP2D6 genotype (phenotype) will be tabulated as specified in [Section 7.2 Demographic and Baseline Characteristics](#).

13 Interim Analysis

No interim analyses are planned.

14 Changes in the Planned Analyses

It has been decided that CYP2D6 phenotype will be tabulated as specified in [Section 7.2](#) Demographic and Baseline Characteristics.

15 References

Not applicable.

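### The SAP replaces the protocol's QTcF-threshold and laboratory counts with new-onset counts, states no denominator, and does not declare the change

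*SAP*

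**What the plan says.** **QTcF thresholds.** Protocol 9.4.2.4 asks, at each time point, for "the number and proportion of subjects with measurement values after double-blind IMP treatment of > 450 msec, > 480 msec, and > 500 msec". It sets no baseline condition. SAP 9.6 keeps the three thresholds but defines the cases as "subjects who do not meet these criteria before the start of double-blind IMP administration and meet the criteria after the start". For these rows it names no time point.

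**Laboratory values.** Protocol 9.4.2.2 states: "The number and proportion of subjects who meet the criteria for clinically significant laboratory value will be determined by treatment group". Again there is no baseline condition. SAP 9.3 counts "subjects who do not meet the criteria for clinically significant laboratory values (Appendix 2) at baseline and meet the criteria after" the start of IMP.

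**Declared changes.** SAP section 14 holds one item: "It has been decided that CYP2D6 phenotype will be tabulated".

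**What the SAP leaves unrestricted.** SAP 9.6 puts no new-onset condition on QTcF change above 30 or 60 msec, on QTcF above 450 msec with more than 10% change, or on the Appendix 3 ECG criteria. It also keeps the normal/abnormal shift table and descriptive change statistics. SAP 9.3 keeps reference-range shift tables, change statistics and a Hy's Law count with no baseline condition.

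**The concern.** A new-onset count answers a different question from a count of everyone who is abnormal on treatment. Either can be right, but the protocol specifies the second, the SAP delivers the first, and nothing tells the reader that the rule changed. The subjects affected are those already over a limit before double-blind dosing.

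Such subjects can exist. The QTcF and laboratory exclusions (Protocol 5.2.2, criterion 10) apply to screening values. The Visit 3 criteria contain no QTcF or laboratory limit, only investigator discretion, and Visit 1 can precede Visit 3 by about five weeks (Protocol Table 1.3-1).

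What is at stake is the reading of the QT and laboratory tables in a phase 2 trial with small arms and no data monitoring committee, where one or two subjects change a percentage visibly. Without a stated denominator, the reported proportion cannot be compared with the one that the protocol describes.

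**Working it through.** **Inputs.** The documents state no figure for this point. They give the planned arm sizes: 120 (20 mg), 120 (placebo) and 30 (10 mg). The 120 reproduces: a difference of 4 with SD 11, two-sided 0.05 and 80% power gives 119.7 per arm by the t calculation. One subject is 1/120 = 0.83 points, or 1/30 = 3.33 points. Baseline abnormality rates are not given.

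**Step 1: which rows count which subject.** The QTcF values are invented, and the SAP condition is applied threshold by threshold.

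| Baseline to on-treatment (msec) | Protocol threshold rows | SAP threshold rows | SAP change > 30 | SAP > 450 and > 10% |
|---|---|---|---|---|
| 445 to 455 | 450 | 450 | no | no |
| 452 to 478 (+26, 26/452 = 5.8%) | 450 | none | no | no |
| 485 to 495 (+10, 2.1%) | 450, 480 | none | no | no |
| 455 to 486 (+31, 6.8%) | 450, 480 | 480 | yes | no |
| 455 to 505 (+50, 11.0%) | 450, 480, 500 | 480, 500 | yes | yes |

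The gap is a rise of at most 30 msec, from above one threshold, that does not cross the next. If the SAP means the thresholds jointly, the 486 and 505 subjects would also leave the higher threshold rows; the text does not settle this.

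**Step 2: effect on a rate.** Let a be new-onset subjects, b those meeting the criterion at baseline, and c those of b who meet it again on treatment. At subject level the protocol rate is (a + c)/N. The SAP rate is a/N, or a/(N − b) if the denominator is restricted. With a = 3 and N = 120:

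| b, c | Protocol | SAP, a/N | SAP, a/(N − b) |
|---|---|---|---|
| 0, 0 | 2.50% | 2.50% | 2.50% |
| 1, 1 | 3.33% | 2.50% | 2.52% |
| 3, 3 | 5.00% | 2.50% | 2.56% |
| 6, 6 | 7.50% | 2.50% | 2.63% |
| 6, 0 | 2.50% | 2.50% | 2.63% |

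The SAP rate is lower, equal or slightly higher, depending on b, c and the denominator.

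**Step 3: per visit or any time (QTcF).** This is a simulation on assumed inputs: a subject effect plus visit error, screening below 450 msec, one baseline ECG, and three on-treatment ECGs (Weeks 2, 4 and 6 in Table 1.3-1). Two end scenarios, for QTcF above 450 msec:

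| Scenario | All, any time | New onset, any time | All, per visit | New onset, per visit |
|---|---|---|---|---|
| Mean 405, SD 15 between and 8 within, no shift | 0.71% | 0.59% | 0.28% | 0.23% |
| Mean 420, SD 18 between and 10 within, shift +5 msec | 14.7% | 11.7% | 7.2% | 5.4% |

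Like for like, the new-onset rate is lower. An any-time new-onset rate, which is how the SAP text most naturally reads, exceeds the per-visit rate that the protocol specifies.

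**Step 4: laboratory values.** Chemistry and haematology have one scheduled on-treatment sample (Week 6, or discontinuation), so Step 3 hardly applies. Assume that 5% meet a criterion at each visit, with baseline-to-Week 6 correlation 0.7 (bivariate normal). The new-onset rate is then 3.0% of all subjects, or 3.0/0.95 = 3.2% of those at risk. Over prevalence 2% to 10% and correlation 0.5 to 0.8, the share dropped is 17% to 56%.

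**Step 5: the laboratory window.** SAP 7.1 and Table 3.4-1 use IMP for the placebo lead-in as well. Counting from the start of IMP in SAP 9.3 therefore takes in the Visit 3 sample. The clinically significant count is protected by its baseline condition; Hy's Law has none. SAP 9.6 specifies double-blind IMP.

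**The case against.** The best defence is that the Protocol (section 9) defers detail to the SAP, that new-onset counting is a standard and sensible way to present treatment-emergent abnormality, and that these are descriptive tables in an exploratory trial. For laboratory values the protocol gives neither a baseline condition nor a window, so the SAP may be seen as filling in detail. All of this is fair. It supports having the new-onset row, but not dropping the protocol's row without saying so.

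A reader might infer that subjects who worsen on drug disappear from the safety tables. The documents do not support that. A rise above 30 msec, or a new higher threshold on the threshold-by-threshold reading, is still counted, and shift tables and change statistics remain. Nor is every dropped subject one who worsened: in the Step 3 model, roughly three to four in ten never exceeded their own baseline.

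A reader might also infer that reported rates must shrink or that the drug signal is diluted. Steps 2 and 3 show that the direction is open. In the simulated end cases the shift/no-shift ratio is higher under new-onset counting (1.55/0.59 = 2.6 against 1.73/0.71 = 2.4; 11.71/6.46 = 1.81 against 14.66/8.75 = 1.68). The absolute gap in the second pair is slightly smaller (5.3 against 5.9 points).

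On Hy's Law, SAP Table 3.4-1 assigns data up to Day 1 to baseline, and ALT or AST above twice the upper limit is excluded at screening. A programmer would probably do the right thing, so that part is a wording correction.

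**Conclusion.** The point stands as an undeclared difference between protocol and SAP in two sets of safety counts, with unspecified denominators and, for QTcF, an unspecified time basis. Its concrete consequence is narrow: a subject already beyond a limit leaves that row, and for QTcF a further rise of 30 msec or less below the next threshold shows in no threshold or change row. For laboratory values, worsening within a category already abnormal at baseline is poorly covered, because the shift table cannot show it and the SAP 9.3 listing covers only the new-onset subjects.

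The size is unknown. Every percentage in Steps 2 to 4 rests on assumed inputs, since the documents give no QTcF distribution and no baseline abnormality rates. The Hy's Law effect would be rare.

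A reader might also conclude that the SAP's safety tables mix case definitions, because vital signs, weight and the Appendix 3 ECG criteria carry no new-onset condition in the body text. Appendices 1 to 3 were not in the text available for this check and may hold baseline-relative conditions, so that is not established. Worth correcting before data lock; it does not touch the primary analysis.

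**What to change.** 1. In SAP 9.6 (QTcF thresholds) and SAP 9.3 (clinically significant laboratory values), report two counts per criterion: (a) all subjects meeting it after the start of double-blind IMP, with QTcF also by time point as the protocol specifies; and (b) new-onset subjects, with the denominator being subjects who did not meet it at baseline and have a post-baseline value.
2. In SAP 9.6, say that the new-onset condition applies to each threshold separately, and whether the earlier value means baseline or any earlier reading.
3. In SAP 9.3, refer to double-blind IMP wherever the window now starts at IMP, including the Hy's Law count.
4. List the new-onset counts in SAP section 14.

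Paired rows for vital signs and the Appendix 3 criteria are optional; no conflict between protocol and SAP has been shown there.

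The cost is SAP wording and slightly longer tables, with no new data. Row (a) will include subjects who were abnormal before treatment, which is why row (b) should stay beside it.
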